1.0 LIST OF ABBREVIATIONS

AE	adverse event
ALT	alanine aminotransferase
ANOVA	analysis of variance
APTC	Antiplatelet Trialists' Collaborative
AST	aspartate aminotransferase
ATC	anatomical therapeutic chemical classification system
BMI	body mass index
BUN	blood urea nitrogen
CHF	congestive heart failure
CI	confidence interval
CPH	Cox proportional hazard
CV	cardiovascular
DMC	data monitoring committee
DVT	deep vein thrombosis
ECG	electrocardiogram
eCLcr	estimated creatinine clearance
FAS	full analysis set
HLT	high level term
IBW	Ideal body weight
ISG	independent statistical group
IVRS	interactive voice-activated response system
IWRS	interactive web-activated response system
LDH	lactate dehydrogenase
MACE	major adverse cardiovascular event
MedDRA	Medical Dictionary for Regulatory Activities
MI	myocardial infarction
NSAIDs	nonsteroidal anti-inflammatory drugs
PE	pulmonary embolism
PT	preferred term
PY	patient-year
QD	once daily
SAE	serious adverse event
sUA	serum uric acid
SAP	statistical analysis plan
SOC	System organ class
TEAE	treatment-emergent adverse event
TIA	transient ischemic attack
ULN	Upper limit of normal
ULT	urate lowering therapy
WHO	World Health Organization

2.0 INTRODUCTION

This document describes the statistical analyses and data presentations to be performed for this multicenter, randomized, double-blind, active-controlled study designed to evaluate the cardiovascular (CV) safety of febuxostat compared with allopurinol in subjects with gout and CV comorbidities.

This statistical analysis plan (SAP) and amendments were developed based on information provided in the following protocol:

- Protocol TMX-67_301 (Amendment 6), dated 27 August, 2013.

Amendment 3 of this SAP will remain sequestered to the blinded team until database lock and un-blinding.

3.0 OBJECTIVES

3.1 Primary Objectives

The primary objective of this study is to compare the risk of predefined major cardiovascular adverse events (MACE) during treatment with febuxostat and allopurinol in subjects with gout and CV comorbidities.

3.2 Study Design

This is a phase 3B multicenter, randomized, double-blind, active-controlled study designed to evaluate the CV safety of febuxostat compared with allopurinol in subjects with gout and significant CV comorbidities. Approximately 7500 subjects will be randomly assigned to study drug treatment.

The overall duration of the study is dependent on the number of predefined MACE. The length of the study is expected to be approximately 9 years. The length of study participation for each subject will vary due to the event driven study design. This study is designed to have a maximum of 624 MACE.

On Study Day 1, eligible subjects will be randomized in a 1:1 ratio to receive either febuxostat once daily (QD) or allopurinol QD. Randomization will be stratified based on baseline renal function (normal renal function or mild renal impairment versus moderate renal impairment). Baseline renal function will be defined using the following criteria based on estimated creatinine clearance (eCLcr):

- Normal renal function: defined as an eCLcr ≥ 90 mL/min.
- Mild renal impairment: defined as an eCLcr 60 to 89 mL/min, inclusive.
- Moderate renal impairment: defined as an eCLcr 30 to 59 mL/min, inclusive.

where estimated creatinine clearance (eCLcr) is calculated using the Cockcroft-Gault formula corrected for ideal body weight (IBW); IBW is 50 kg for males and 45.5 kg for women, plus 2.3 kg for each inch in height >5 feet (60 inches)]:

[figure not shown]
$$eCLcr = \frac{(140 - \text{Age}[\text{yr}]) \times (\text{IBW}[\text{kg}]) (\text{women multiply by } 0.85)}{72 \times (\text{serum creatinine} [\text{mg/dL}])}$$

Subjects randomized to febuxostat will initially receive the 40 mg dose QD. Subjects will remain on 40 mg for the remainder of the study if their serum uric acid (sUA) is <6.0 mg/dL at the Week 2 Visit. If their sUA is ≥ 6.0 mg/dL at the Week 2 Visit they will receive febuxostat 80 mg QD at the Week 4 visit, and will remain on this dose for the remainder of the study.

Subjects randomized to allopurinol who have normal renal function or mild renal impairment will initially receive allopurinol 300 mg QD with the dose increased in 100 mg increments monthly until either a sUA <6.0 mg/dL or an allopurinol dose of 600 mg QD is achieved. Subjects randomized to allopurinol who have moderate renal impairment will initially receive allopurinol 200 mg QD with the dose increased in 100 mg increments monthly until either a sUA

<6.0 mg/dL or an allopurinol dose of 400 mg QD is achieved. The randomization and dosing schema are displayed in Figure 3.a.

Figure 3.a Dose Titration Based on sUA Response and By Baseline Renal Function in the First Three Months of the Study

Serum urate levels will be unblinded to the investigator and Takeda during the first 10 weeks of the study to facilitate dose increases based on sUA response. After the Week 10 Visit, sUA measurements will be blinded to Takeda and the investigator. The interactive voice-activated response system/interactive web-activated response system (IVRS/IWRS) will manage the treatment assignment after randomization and throughout the study medication treatment.

To maintain the double-blind nature of the study, febuxostat and allopurinol tablets will be over-encapsulated and matching placebo capsules will be manufactured which are identical in appearance. Subjects will orally self administer 2 capsules each morning in the appropriate combination for their assigned dose and treatment.

Subjects currently on urate-lowering therapy (ULT) will discontinue treatment at the Day -7 Screening Visit, and will begin colchicine 0.6 mg QD for gout flare prophylaxis. Subjects not on ULT will begin colchicine 0.6 mg QD on the Day 1/Randomization Visit. All subjects will receive gout flare prophylaxis for the first six months of the study medication treatment period. Alternatively, if colchicine is not tolerated and the subject's eCLcr is ≥50 mL/min, they will be administered naproxen 250 mg twice daily with lansoprazole 15 mg QD. If a subject has been

maintained on an appropriate dose (as determined by the investigator) of another proton pump inhibitor other than lansoprazole, he/she may continue treatment with it during this study. In instances when subjects should not receive colchicine or naproxen, other nonsteroidal anti-inflammatory drugs (NSAIDs) or prednisone may be provided at the investigator's discretion.

Following the Day 1/Randomization Visit, subjects will return for study visits during the first 3 months of the study based on the subject's sUA response. Once a subject's sUA <6.0 mg/dL, there will be no further visits until Month 3.

All subjects will return at Week 2 for measurement of sUA and all subjects will return for a Week 4 and Month 3 visit. If the Week 2 sUA level is <6.0 mg/dL, the subject will be dispensed study medication at Week 4, and the next visit will occur at Month 3. If the Week 2 sUA level is ≥ 6.0 mg/dL, the subject will be dispensed study medication at Week 4, and the next visit will occur at Week 6.

For the subset of subjects who have a Week 6 visit, if the Week 6 sUA level is <6.0 mg/dL, the subject will be dispensed study medication at Week 8, and the next visit will occur at Month 3. If the Week 6 sUA level is ≥ 6.0 mg/dL, the subject will be dispensed study medication at Week 8 and the next visit will occur at Week 10.

For the subset of subjects who have a Week 10 visit, the subject will be dispensed study medication at the Month 3 visit. After the Month 3 visit, no further dose adjustments will be made. All subjects will have Month 3 and Month 6 visits.

Following the Month 6 visit, all subjects will have visits every 6 months for the duration of the study. In addition, subjects with moderate renal impairment (eCLcr <60 mL/min) and/or subjects who are elderly (≥ 65 years of age) will have visits at Month 9 and Month 15 to monitor liver function tests. Subjects who are withdrawn from study medication treatment but have not withdrawn consent will be followed via phone calls every 2 months until the end of the study or until the subject experiences a CV event that is positively adjudicated as a MACE.

A Data Monitoring Committee (DMC) will periodically review results obtained in the study, including results at 3 planned interim analyses. They will monitor the progress and the on-going safety of subjects enrolled into the study. An Independent CV Endpoints Committee will be established to prospectively review all suspected CV events using blinded data. A periodic review of all serious adverse events and specific CV adverse event terms will be performed by the Chair of the CV Endpoints Committee. The Chair, not the sponsor, will designate cases for comprehensive review by the CV Endpoints Committee. All investigational sites will be required to collect relevant clinical information required for adjudication of all deaths and potential CV serious adverse events (SAE).

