6.6 Study Drug Exposure and Compliance

Summaries of study drug exposure, study participation, and compliance will be presented by treatment group and based on the FAS. No inferential statistics will be presented.

A subject's extent of drug exposure will be calculated as the duration of treatment in the double-blind treatment period. Duration of study drug exposure in days will be defined as (date of last dose - date of first dose + 1). If the date of last dose is missing and a subject has discontinued from the study, then, for summary purposes, the last dose date will be estimated as the last drug dispense date plus the number of days in the dosing interval or date of last contact, whichever comes first. The study participation will begin on the day of randomization and end on the day of last contact. Duration of study participation in days will be defined as (date of last contact - date of randomization + 1). For subjects who report a MACE event after treatment discontinuation, the start date of the event will be used as the date of last contact.

Treatment duration and study participation will be summarized overall and by treatment group using descriptive statistics and subject counts at the intervals: Day 1 to Day 364 [Year 1], Day 365 to Day 728 [Year 2], Day 729 to Day 1092 [Year 3], Day 1093 to Day 1456 [Year 4], Day 1457 to Day 1820 [Year 5], Day 1821 to Day 2184 [Year 6], and \geq Day 2185 [\geq Year 6]. In addition, within each treatment group, the duration of treatment by each dose will be summarized.

Study drug compliance will be calculated and summarized with descriptive statistics and subject counts within compliance categories (<80%, 80–<90%, \geq 90%). Compliance (%) will be calculated as the number of capsules taken divided by two times the number of days on drug.

The number and percentage of subjects on the final dose and with dose adjustment from initial dosing will be summarized by treatment group. The final doses based on sUA response and by baseline renal function are summarized in [Figure 3.a](#).

The number and percentage of subjects with use of each type of prophylactic medication based on the initial dosing and dose adjustment from initial dosing will be summarized by treatment group. In addition, descriptive statistics on the total number of days (date of last dose - date of first dose + 1) of prophylactic dosing will be summarized by treatment group.

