6.12 Safety Analysis

Safety will be assessed by evaluating the incidence of adverse events including cardiovascular adverse events such as predefined MACE composite, and evaluating ECGs; laboratory tests and vital signs. A CV Endpoints Committee blinded to treatment assignment will adjudicate potential cardiovascular adverse events and each death to determine if it meets MACE criteria. The procedures and rules of adjudication of these events by the CV Endpoints Committee is described in a separate charter.

For the primary, secondary, and additional safety endpoints, time to event will be the time from the date of randomization or the date of last dose of study medication to the date of first occurrence of any event in the respective endpoint. If a subject reports an event for a given safety endpoint after treatment discontinuation, the reported event will be counted toward the treatment to which they were randomized. Subjects who are lost to follow-up during the study or who do not exhibit an episode of an event for the specific safety endpoint throughout the study will be censored at the day of last contact.

All safety endpoints will be analyzed using the Full Analysis Set (FAS). The FAS will consist of all subjects who were randomized and received at least one dose of double-blind study medication. Non-inferiority will be assessed only for the primary safety endpoint.

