6.12.3 Other Safety Endpoints

The following additional safety endpoints will also be assessed:

- The time from randomization to the first occurrence of any event in the pre-defined MACE composite plus any of the following events:

- Urgent Cerebral revascularization [non-elective].
- Hospitalized congestive heart failure (CHF).
- Arrhythmias not associated with ischemia.
- Venous and peripheral arterial thromboembolic events; eg, Deep Vein Thrombosis (DVT) and Pulmonary Embolism (PE).
- Transient Ischemic Attack (TIA).
- The time from randomization to the occurrence of all-cause death,
- The time from randomization to the occurrence of all-cause death during treatment (from randomization to last dose of study medication),
- The time from last dose of study medication to the occurrence of all-cause death,

Survival analysis using the CPH model will be performed for these additional endpoints. Parameter estimates and a 2-sided 95% CI for the hazard ratio will be computed.

Kaplan-Meier plots will also be presented by treatment group.

The following other additional safety analyses will also be performed:

- The number of subjects with first occurrence of predefined MACE that occur no more than 30 days after a subject's last dose of study drug and the associated incidence rate by 100 patient-years of exposure along with 95% confidence intervals will be summarized by treatment group. The 95% CIs will be calculated based on the Poisson distribution. For a given treatment total patient-years (PY) of exposure will be calculated by summing across all subjects the total number of days on the treatment and dividing by 365.

The same analysis will be performed for each component of the MACE composite.

- Mortality analyses for the overall and by CV and Non-CV cause. The total number deaths and the death rate with 95% CI will be presented. The 95% CIs for the death rate will be calculated based on the Binomial distribution using exact method.
- The number and percentage of subjects with first occurrence of a pre-defined MACE composite will be presented by number of days in the study.
- List of CV risk factors for subjects with a predefined MACE composite comprising diabetes, hypertension, hyperlipidemia, obesity, and smoking will be provided by treatment group. Listings include subject number, age, gender, baseline renal function, primary MACE component, disposition, primary reason for discontinuation if disposition is early term, and CV risk factors.

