At the DMC meeting on ^{PPD} [REDACTED], the 75% interim analysis results based on 468 adjudicated MACE for the primary MACE endpoint to assess cardiovascular safety was reviewed by the DMC. At the DMC meeting on ^{PPD} [REDACTED], the DMC informed Takeda that the non-inferiority criterion for the primary endpoint was met at the 75% interim analysis conducted in ^{PPD} [REDACTED]. According to the study design, the study should have been stopped and the non-inferiority of febuxostat relative to allopurinol with regard to cardiovascular risk should have been declared. However the DMC recommendation was to continue the trial without modification until the maximum 624 unique events were achieved to further assess all cause mortality (which was not a protocol specified endpoint) and CV mortality (which is specified only as a component of the MACE endpoint). Takeda agreed to follow the DMC recommendation and continue the study.

Based on the group sequential design, the 75% interim analysis will be the primary analysis for the primary MACE endpoint for the purpose of statistical inference. The continuation of the study to protocol-specified maximum events (624 unique MACE) is for the assessment of all cause mortality and CV mortality. The analyses of all cause mortality and CV mortality with and without death events after discontinuation of treatments will be added to the end of study analysis. An updated sensitivity analysis for the primary MACE endpoint based on 624 unique MACE will also be conducted to provide additional supportive evidence for the primary endpoint.

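### Follow-up and censoring rules built for time to first MACE are applied unchanged to the death endpoints, so off-drug survivors can be censored at a non-fatal MACE while later reported deaths still count

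*SAP*

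**What the plan says.** Four parts of the SAP combine.

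- **Contact (3.2).** Subjects who are off drug but still consenting are called every 2 months "until the end of the study or until the subject experiences a CV event that is positively adjudicated as a MACE". Three of the four MACE components in section 4.1 are non-fatal.
- **Last contact (6.6).** Participation is defined first: "The study participation will begin on the day of randomization and end on the day of last contact". For a MACE reported after the subject has stopped drug, "the start date of the event will be used as the date of last contact".
- **Censoring (6.12).** One rule covers the primary, secondary and additional safety endpoints. A subject with no event "for the specific safety endpoint throughout the study will be censored at the day of last contact". Events reported off drug are kept in the randomized arm: "If a subject reports an event for a given safety endpoint after treatment discontinuation, the reported event will be counted toward the treatment". Death has no rule of its own.
- **Mortality endpoints (4.2, 4.3, 6.12.3, 6.13).** CV death is analysed as a MACE component, and all-cause death from randomization. A further endpoint is "The time from last dose of study medication to the occurrence of all-cause death". After the 75% interim analysis, section 6.13 states: "The continuation of the study to protocol-specified maximum events (624 unique MACE) is for the assessment of all cause mortality and CV mortality". Those analyses are to be run "with and without death events after discontinuation of treatments".

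Sections 3.2 and 6.12 also require sites to collect what is needed to adjudicate every death, and the endpoints committee to adjudicate each one.

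**The concern.** Stopping contact at the first MACE loses nothing when first MACE is the endpoint. When death is the endpoint, it ends scheduled contact just when the risk of death is probably raised. The SAP took on all-cause death endpoints in Amendment 2, and Amendment 3 made mortality the reason for continuing, but the current censoring text still has only the one rule.

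Two problems follow if the 6.6 date is used for censoring. Survivors leave the risk set at a prognostic event, so the censoring may be informative. Deaths that become known later still enter on their own dates, so how long a subject is followed depends on whether that subject died. Time from last dose to death is the most exposed, because every affected subject is in it and every affected MACE falls inside its time window. All-cause death during treatment is untouched, because it ends at last dose.

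**Working it through.** **1. Trace of the rules.** Take two off-drug subjects, each with a non-fatal MI at time m after stopping drug. One dies later, at time d, and the site learns of it. The other is alive at study end, time E.

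| Endpoint | Later death, reported | Survivor |
|---|---|---|
| First MACE | event at m | event at m |
| All-cause death | event at d | censored at m, if 6.6 governs; alive to E in fact |

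The first row is correct for both subjects. In the second row the time from m to d is counted for the subject who died, and the time from m to E is dropped for the survivor.

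**2. Anchor on the plan's own figure.** Section 5 inputs: N = 7500, MACE rate λ = 0.028 per year, drop-out 0.10 per year, accrual 2.5 years, maximum participation 5 years, so follow-up is taken as uniform on 2.5 to 5 years. For a total exit rate x, let E(x) = (e^(−2.5x) − e^(−5x)) / (2.5x).

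- x = 0.028 + 0.10 = 0.128; E = (e^(−0.32) − e^(−0.64)) / 0.32 = 0.621.
- Expected first MACE = 7500 × 0.028/0.128 × (1 − 0.621) = 621, against the plan's 624.

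**3. Subjects whose calls stop at a non-fatal off-drug MACE.** The SAP gives no drug-discontinuation rate and no fatal share. Assumed: discontinuation δ of 8% to 30% per year and 20% to 40% of first MACE fatal. First MACE on drug = 7500 × 0.028/(0.128 + δ) × (1 − E(0.128 + δ)); the remainder of the 621.1 are off drug.

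| δ | E | On-drug MACE | Off-drug MACE | Non-fatal share | Subjects |
|---|---|---|---|---|---|
| 0.08 | 0.464 | 541.6 | 79.5 | 0.60 | 48 |
| 0.20 | 0.301 | 447.8 | 173.3 | 0.70 | 121 |
| 0.30 | 0.211 | 387.3 | 233.8 | 0.80 | 187 |

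A simulation that adds non-CV death (assumed 1% to 2% per year) gives 44 to 186 subjects with section 5 follow-up. It gives 53 to 207 with follow-up uniform on 0 to 6.45 years and no loss.

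**4. Deaths outside scheduled contact.** With an assumed death hazard of 6% to 20% per year after a non-fatal MACE, the same simulation gives about 3 to 56 deaths. That is 0.5% to 11% of all deaths and 4% to 25% of deaths after stopping drug. At central inputs (δ = 0.20, fatal share 0.30, post-MACE hazard 0.15, non-CV death 0.015) the share of all deaths is roughly 3.5% to 4.6%. A second model, with a 50% to 70% non-fatal share, 10% to 20% yearly discontinuation, 2.5% yearly mortality raised 2- to 4-fold after a non-fatal MACE, and follow-up of up to 7 years, gives about 60 to 220 subjects, 4 to 39 deaths and 0.6% to 4.1% of all deaths. These are illustrative ranges, not bounds.

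**5. Effect on the hazard ratio (febuxostat to allopurinol).** Central inputs, section 5 follow-up, 1,500,000 simulated subjects per arm. Each cell shows full follow-up, then follow-up cut at the off-drug MACE.

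| Assumed truth | All-cause, from randomization | All-cause, from last dose |
|---|---|---|
| Arms equal | 1.002; 1.002 | 0.992; 0.990 |
| Post-MACE death 1.5-fold on febuxostat | 1.061; 1.050 | 1.076; 1.035 |
| Post-MACE death 1.5-fold on allopurinol, non-CV death 1.3-fold on febuxostat | 1.100; 1.119 | 1.083; 1.153 |
| Arms equal; 70% of later deaths reported in one arm, 40% in the other; only survivors and unreported deaths cut at the MACE | 1.000; 1.009 | 0.999; 1.034 |

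Monte Carlo error of the log hazard ratio is about 0.004 and 0.008 in the two columns; differences within a run are paired and more precise. If every later death is known and only survivors are cut, the ratio moves by 0.004 or less. At N = 7500 the standard error of the log hazard ratio is about 0.08 (all-cause) and 0.15 (from last dose). The largest shifts in the table are ln(1.119/1.100) = 0.017, or 0.2 standard errors, and ln(1.153/1.083) = 0.063, or 0.4 standard errors. The direction differs between scenarios.

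**The case against.** The strongest reply is that 6.6 states its rule while defining participation duration, and 6.12 does not refer back to it. That is fair: whether the MACE date governs censoring is an inference. But 6.12 relies on a day of last contact, and 6.6 is the only place that assigns one after an off-drug MACE. Even on the narrow reading, calls stop under 3.2.

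Second, sites must collect information on all deaths and the committee adjudicates each one, with no limit to the time before a first MACE. This softens the gap, and if it works perfectly the modelled shift is negligible. It sets no contact after a MACE, however, and does nothing for the survivors' censoring date.

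Third, vital-status procedures belong to the protocol, which is not at hand. Their absence from the SAP is therefore not the point. Coverage cannot be presumed either, since 6.13 says all-cause mortality was not a protocol-specified endpoint. The SAP's own censoring text needs a rule for death in any case.

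Fourth, the effect is probably small, and the between-arm imbalances used above have no basis in the document. That stands.

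A reader might infer more: that the mortality hazard ratio is biased in a known direction, that the non-inferiority result is in doubt, or that nobody was followed after a MACE. The document supports none of these. The direction depends on unknown differences between arms, first MACE is complete under these rules, and the stopping rule in 3.2 concerns scheduled calls to off-drug subjects only. What happens to a subject who stops drug after an on-drug MACE is a detail the protocol may settle. The spill-over to the APTC endpoint arises only when the first MACE is unstable angina, and is secondary.

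**Conclusion.** The point holds as a mismatch between rules and endpoints. Read literally, 3.2, 6.6 and 6.12 together censor off-drug survivors at a non-fatal MACE while counting later reported deaths, in the mortality analyses that 6.13 gives as the reason for continuing. The primary MACE analysis and the alpha spending are unaffected.

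Size and direction of any bias cannot be derived from the document. Under the assumed rates, several dozen to about two hundred subjects are involved and the hazard ratio shifts are about half a standard error or less, with no meaningful shift when the arms do not differ in post-MACE mortality or death reporting. The point deserves correction because mortality carries the weight of the continued study and the correction is cheap, not because a large distortion has been shown.

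**What to change.** 1. In 6.6 and 6.12, limit the rule that equates the MACE start date with last contact to the participation summary and the first-MACE analyses.
2. For all-cause death, CV death and death from last dose, censor at the last date known alive, using all vital-status information available to study end, including after a non-fatal MACE. This helps only as far as such information exists. Otherwise the last date known alive is close to the MACE and known later deaths still stand alone.
3. Report by arm the number of off-drug subjects with a non-fatal MACE whose vital status at study end is unknown.
4. Add a sensitivity analysis that ends follow-up for deaths and survivors alike at the last scheduled contact. State that it discards some known deaths and can itself differ from full follow-up, as the table under the third step of the hazard ratio scenarios illustrates.
5. If the protocol or study operations allow, obtain vital status for these consenting subjects. Because Amendment 3 is sequestered from the blinded team until database lock, this needs a channel that does not unblind that team; SAP text alone cannot start it.

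The cost is a few SAP sentences, one more analysis and possibly incomplete vital-status data where calls stopped years earlier. The primary analysis, the 624-event maximum and the alpha spending do not change.
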